intention to treat; any missing data will be addressed with the technique of multiple imputation (Rubin, 2004), generally recognized as best for handling missing data (Little et al., 2012).

d. Early stopping rules.

N/A

8. Risks

a. Medical risks, listing all procedures, their major and minor risks and expected frequency.

Two primary instrumental techniques will be utilized, EEG and fNIRS, neither of which have major risks associated. Since EEG neurofeedback is a passive learning process, there is a limit to the extent of negative reactions that can arise as a result of its use (Collura, 2014). Collura discusses two types of abreactions (expression and consequent release of a previously repressed emotion) that might occur as the brain learns self-regulation and normalizes through neurofeedback training. One type of such reactions could be if neurofeedback training results in normalization of a compensatory mechanism that has helped the client cope with particular stresses or other dysregulations. An example could be if a chronically anxious client exhibits excess alpha as a coping mechanism to reduce anxiety. If through neurofeedback training, alpha levels normalize and reduce this coping mechanism, anxiety levels could increase. The long-term goal of neurofeedback is to allow the client to develop healthier circuitry patterns that do not rely on maladaptive patterns in order to cope. The second type of possible abreaction could be the resurfacing of psychological trauma that had been dealt with through coping mechanisms once these coping mechanisms are lessened through more normalized brainwave activity. Another possible negative response is the development of negative effects from current medication regimens as the trainee's brain learns to self-regulate and normalize.

Near-infrared spectroscopy (NIRS) is a relatively new investigational tool. Although no adverse effects have been reported, it is possible that effects not yet reported may occur. The LED light in the NIRS devices used to make the measurements has low power (within the ANSI limit for long-term exposure to infrared light). Thus far, no hazard to patient, staff or third party has been observed. Should any adverse effects be observed during the study, they will be immediately reported to the IRB. NIRS monitoring requires coupling "optodes" (optical sensors) to the skin on the scalp. This is achieved by fastening the optodes to a cap, placing the cap over the head and holding it in place with a strap placed under the chin or behind the head. The subject's hair may need to be parted in the location of the optodes to provide better coupling to the skin. The procedure does not cause pain or distress. Subjects will be asked to keep their head relatively still for several periods of up to approximately 10-15 minutes each while performing the tasks. However, the NIRS device will be made as insensitive as possible to head motion, and hence strict subject compliance is not essential. Fatigue from performing the tasks is the most likely risks in this study.

Date: November 11, 2021
Principal Investigator: [name]
Application Number: IRB00242136
NCT# NCT04290988
Study Title: Circuitry Assessment and Reinforcement Training Effects on Recovery (CARTER)

There are no known risks to behavioral speech-language therapy. Participants may experience fatigue, frustration, or boredom during the tasks. Participants will be offered breaks, as needed.

In the event of a global pandemic due to an outbreak of a highly contagious viral infection (e.g., COVID-19), participants have some risk of transmission and contraction of the virus upon participating in in-person study tasks due to being in contact with (or in close proximity to) other people who are potentially infected or who are carriers of the virus and by being potentially infected with (or carriers of) the virus themselves. So, in the event of a pandemic of this nature, precautions will be taken as outlined below.

b. Steps taken to minimize the risks.

Participants will be carefully screened prior to being scheduled, to assure that they meet study criteria. EEG neurofeedback sessions will be closely supervised to monitor for any adverse reactions. The participant may stop testing or the intervention at any time. On any given session, if the patient experiences significant frustration, anxiety, or fatigue, that session may be terminated early. Short-term abreaktions will be monitored closely. Those with a history of severe psychological trauma and severe psychological conditions will be excluded from the study.

In the event of a global pandemic (such as COVID-19 outbreak), precautions will be taken to reduce the spread of infection related to the viral outbreak. This includes the following:

1. Remote testing will become the primary mode of testing.
2. If remote testing is not feasible, we will perform home visits whenever possible to limit contact of participants with others at the hospital setting.
3. We also have the option of using the STAR Car, a mobile lab space (wheelchair-accessible van) to reduce the number of people on-campus.
4. If remote testing and/or home visits are not possible, participants may be seen at their outpatient appointment scheduled for clinical follow-up.
 - a. For outpatient appointments, we will limit session room attendance to the participants only (rather than allowing family members to be present in the testing room) and one staff member to administer the session.
 - b. We will also limit lab staff members on-site to essential personnel only, per JHU guidelines.
5. We will screen participants by phone to inquire about recent symptoms and exposure to (e.g., related to COVID-19) before any in-person appointments. Per JHU guidelines, we will defer any appointments (i.e., if any active symptoms are present, we will defer any in-person appointments).
6. Staff will reference JHU policies for self-screening and will defer any in-person or on-campus activities if they suspect that they have any active symptoms (e.g., related to COVID-19).
7. For all in-person visits, we will disinfect test and treatment materials (computers, caps, tablets, pens), devices (EEG amplifier, electrode leads, fNIRS system, optodes) and surfaces (tables, doorknobs) before and after each session.

Date: November 11, 2021
Principal Investigator: [name]
Application Number: IRB00242136
NCT# NCT04290988
Study Title: Circuitry Assessment and Reinforcement Training Effects on Recovery (CARTER)

8. During in-person visits, staff and participants will wear disposable or cloth face masks, eye shields, and disposable gloves per JHU guidelines.
9. Participants will be asked to use hand hygiene at the beginning of in-person test and treatment sessions before handling equipment; this may include washing hands with soap and water or using hand sanitizing gel/foam approved by the university.

c. Plan for reporting unanticipated problems or study deviations.

Adverse events will be monitored during the entire visit by the study team. The families will be given telephone numbers of study team as well. The study physician ([name]) will be notified immediately if any adverse events are reported. Adverse events will be monitored until they are resolved or clearly determined to be due to a subject's stable or chronic condition or intercurrent illness. Medical care will be provided, as defined in the informed consent, for any adverse event related to trial participation. All adverse events, regardless of intensity or causality, will be recorded in the study documentation and reported to the JHMI IRB. Any serious adverse events will be reported to the JHMI IRB within 24 hours.

Plan for dealing with incidental findings: qEEG will be reviewed by a neurologist if any concerning abnormal findings are present (e.g., possible seizure activity). If an incidental finding is discovered, the site PI ([name]) will call the patient, and arrange to see the patient in clinic on a timely basis to discuss the finding and the plan for medical follow-up (if any). As [name] is the neurologist of the PPA and stroke patients, she will provide care for most of the findings seen on behavioral and physiological assessments, but will refer the patient to other physicians as appropriate.

d. Legal risks such as the risks that would be associated with breach of confidentiality.
Participation in this study should not put participants in any legal risk, even in the case of a breach of confidentiality. We will undertake every effort to keep the information in the study confidential. Participants will be assigned a code number for all data in order to keep the information confidential. The computers on which the information will be stored are password protected. Everybody involved in the study will have completed the appropriate HIPAA training and are fully aware of confidentiality issues. No names will be included in any publications resulting from this work.

e. Financial risks to the participants.

No financial risk is involved. There will be no cost for the therapy or any procedures.

9. Benefits

a. Description of the probable benefits for the participant and for society.

We cannot ensure that this research will provide any direct, sustainable benefit to the participants. Participant's language skills may or may not improve from the training.

Date: November 11, 2021

Principal Investigator: [name]

Application Number: IRB00242136

NCT# NCT04290988

Study Title: Circuitry Assessment and Reinforcement Training Effects on Recovery (CARTER)

Completion of this project will result in better understanding whether and how EEG neurofeedback may help individuals with PPA or post-stroke aphasia. This project may provide a way to treat language in individuals with PPA or post-stroke aphasia. If we find that a participant shows more improvement in naming during the active feedback than the sham feedback, he or she will be offered up to 15 more sessions of the active feedback at no cost. He or she may accept or decline the additional feedback sessions.

10. Payment and Remuneration

a. Detail compensation for participants including possible total compensation, proposed bonus, and any proposed reductions or penalties for not completing the protocol.

Participants will not be paid to participate in the study. There is no penalty for not completing an assessment or treatment session.

11. Costs

a. Detail costs of study procedure(s) or drug (s) or substance(s) to participants and identify who will pay for them.

There is no cost to the participants for participating in the study.

12. References

Banerjee S. & Argáez, C. (2017). *Neurofeedback and biofeedback for mood and anxiety disorders: A review of clinical effectiveness and guidelines*. Ottawa (ON): Canadian Agency for Drugs and Technologies in Health. Available from: <https://www.ncbi.nlm.nih.gov/books/NBK531603/>

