Visit 1: Screening and Baseline Behavioral Assessment. These sessions involve language testing with the OANB (first), picture description, and COWA. This will be the baseline language testing for the first intervention period. Participants with an OANB score that exceeds an average of 80% accuracy will be excluded to leave at least a 20% improvement margin. That is, participants who already score close to ceiling may have limited room for naming improvement. During the first visit, participants will undergo screening assessments. This will determine if they are a candidate for the treatment. If the participant passes the initial screening portion, informed consent will be obtained.

Visit 2: Baseline qEEG and fNIRS. Participants will undergo qEEG brain mapping assessment to obtain baseline EEG analysis to assess brainwave patterns and to identify areas of abnormality compared to normative database of same-age healthy peer group to establish appropriate training goals for neurofeedback sessions. Participants will also undergo fNIRS assessments.

Visit 3-17: Intervention Phase I. These sessions will include the treatment sessions for the first intervention period. Prior to the start of treatment, participants will be randomly assigned to receive either “neurofeedback then sham” or “sham then neurofeedback.” For example, if a participant is randomly assigned to receive “neurofeedback then sham,” the first intervention period of 15 sessions will be neurofeedback training and the second intervention period will be 15 sessions of sham training. Participants will undergo treatment sessions within each intervention phase at a frequency of 2-5 sessions per week as their schedule allows. At each visit within this intervention phase, participants will also receive speech-language therapy (VNeST).

Date: November 11, 2021
Principal Investigator: [name]
Application Number: IRB00242136
NCT# NCT04290988
Study Title: Circuitry Assessment and Reinforcement Training Effects on Recovery (CARTER)

Visits will take approximately 45-minutes for EEG biofeedback training plus an additional 45-minutes for speech-language therapy.

Visit 18: 1-week Post-Intervention Assessment (following Intervention Phase I). This visit will involve post-treatment language testing, qEEG and fNIRS.

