Visit 19-33: Intervention Phase II. These sessions will include the treatment sessions for the second intervention period. The opposite neurofeedback condition will be implemented here. For example, if a participant is randomly assigned to receive “neurofeedback then sham,” the second intervention period will be 15 sessions of sham training. Participants will also receive speech-language therapy (VNeST) during each visit within this intervention phase. Each visit will take approximately 45-minutes for EEG biofeedback training plus an additional 45-minutes for speech-language therapy.

Visit 34: 1-week Post-Intervention Assessment (following Intervention Phase II). This visit will involve 1 week post treatment language testing, qEEG and fNIRS.

Visit 35: Five-Week Post-Intervention Assessment (following Intervention Phase I and II). This visit will include follow-up language testing, qEEG and fNIRS at 5-weeks post-second intervention period.

b. Study duration and number of study visits required of research participants.

Participants will receive treatment for 3-6 weeks (2-5 sessions in a week: total 15 sessions) for each intervention period. There will be one active neurofeedback treatment period and one sham treatment period for each participant with a 1-week washout period in between the two treatment phases. Participants will receive speech-language therapy (VNeST) at each treatment visit (during both active and sham intervention phases). We will assess the participants at baseline and at 1-week follow-up appointments after each treatment period. Participants will undergo a 5-week follow-up appointment following the second treatment period. Study duration will be approximately 15-20 weeks, and the number of visits for each participant will be 35.

c. Blinding, including justification for blinding or not blinding the trial, if applicable.

Randomization and Blinding

The study is to be conducted in a double-blind manner. The participants and the clinician performing the behavioral and physiological assessments will not know the treatment assignment. The PI will have access to the unblinded list of randomization codes and treatment assignments. Technicians performing the active and sham neurofeedback sessions will utilize pre-developed scripts for both active and sham conditions to standardize the prompts utilized within each arm of the study. Participants will answer survey questions throughout each

Date: November 11, 2021

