The primary outcome variable will be the change in number of Content Units (CU) in picture description from baseline to 1-week post-treatment. Hypothesis 1A is: Participants will show greater improvement in CU from baseline to 1-week post treatment, during the EEG neurofeedback condition than during the sham condition.

To test Hypothesis 1A, we will subtract baseline CU from 1-week post-treatment CU, for each condition. We will use a paired t-test to determine if, as a group, patients showed greater increase in CU during the neurofeedback condition compared to the sham condition. We will also carry out paired t-tests for post-stroke aphasia and PPA separately, to determine if the effect was greater in one group.

b. Secondary outcome variables

Hypothesis 1B-F take the form of: Participants will show greater improvement in [outcome variable] from baseline to 1-week post treatment, during the EEG neurofeedback condition than during the sham condition.

To test each hypothesis 1B-F, we will subtract baseline score from follow up scores (1-week post-treatment), for each condition. We will use paired t-tests to determine if, as a group, patients showed greater improvement during the neurofeedback condition compared to the sham condition, at each follow-up. We will correct for multiple comparisons using a Bonferroni correction.

Hypothesis 2A is: We will be able to identify baseline characteristics (demographics and baseline severity measures, as well as qEEG abnormalities) that influence change in the primary outcome measure (change in CU in picture description from baseline to 1-week post-treatment).

To test this hypothesis, we will carry out multivariable linear regression, with the dependent variable (change in CU in picture description from baseline to 1-week post-treatment), and independent variables of age, baseline CU, baseline OANB, baseline COWA, baseline sleep quality, baseline S-anxiety (STAI), brainwave activity (absolute power, peak amplitude frequency) in each frequency band (alpha, beta, theta, delta, gamma) on qEEG.

Hypothesis 2B is: We will be able to identify changes in secondary outcome measures and changes in qEEG that correlate with the primary outcome measure (change in CU from baseline to 1-week post-treatment). These results will allow us to identify variables to explore the mechanisms of the effects.

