To test this hypothesis, we will compare baseline and follow-up z-scores for coherence in each of the frequency bands (alpha, beta, theta, delta, gamma) by subtracting the absolute value baseline z-score from the absolute value follow-up z-scores for coherence in each condition. We will use paired t-tests to determine if, as a group, patients showed greater improvement during the neurofeedback condition compared to the sham condition, at each follow-up. We will correct for multiple comparisons using a Bonferroni correction. We will also carry out paired t-tests for post-stroke aphasia and PPA separately, to determine if the effect was greater in one group.

c. Statistical plan including sample size justification and interim data analysis

Statistical Analyses

Statistical tests to evaluate each hypothesis are described above. No interim data analyses are planned, although we will become unmasked to condition after each participant completes the 5 week follow-up

Sample Size Determination

This study is a novel application of neurofeedback for treatment of aphasia, and we have no preliminary data to guide a power analysis. However, we will use this preliminary cross-over study (with each patient as their own control) to identify effect size (if any), in order to plan a randomized, double-blind, parallel, sham-controlled trial. For this preliminary trial, we plan to study 8 patients per year with post-stroke aphasia, and 8 patients per year with PPA, based on our other ongoing trials of post-stroke aphasia and PPA, in which we have found that it is feasible to recruit and retain 8-10 of each per year. We hope to obtain a total of 40 patients with post-stroke aphasia and 40 with PPA over 5 years, to obtain preliminary data for a multicenter, randomized, double-blind, parallel, sham-controlled trial, if the preliminary results are positive.

Missing Data

We plan to minimize missing data by avoiding prolonged intervals between conditions. Most of the study will take place within 7-11 weeks, with each person scheduled to have a 5 week follow up to determine if any changes are long-lasting. To minimize biases, analyses will be by

Date: November 11, 2021
Principal Investigator: [name]
Application Number: IRB00242136
NCT# NCT04290988
Study Title: Circuitry Assessment and Reinforcement Training Effects on Recovery (CARTER)

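### No blocking or stratification of treatment order by diagnosis is described, and the separate stroke and PPA t-tests have no period adjustment, so an uneven order would carry part of any period difference into them

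*Combined protocol and SAP*

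**What the plan says.** **Allocation.** Section 4a (Visit 3-17, Intervention Phase I) states: "Prior to the start of treatment, participants will be randomly assigned to receive either" of the two orders, active first or sham first. Section 2 says the same in other words. Section 4c, Randomization and Blinding, adds only who may see the list: "The PI will have access to the unblinded list of randomization codes and treatment assignments". No section gives an allocation ratio, a blocking scheme, a stratification factor or a method of generating the list.

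**Analysis.** The primary test in section 7a is a comparison of change scores: "We will use a paired t-test to determine if, as a group, patients showed greater increase in CU during the neurofeedback condition" compared with sham. The same section continues: "We will also carry out paired t-tests for post-stroke aphasia and PPA separately, to determine if the effect was greater in one group". Section 7b repeats the separate tests for Hypotheses 3A and 3B. No period or sequence term appears anywhere in section 7.

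**Numbers.** Section 7c sets the target by diagnosis: "We hope to obtain a total of 40 patients with post-stroke aphasia and 40 with PPA over 5 years". It gives no effect size, standard deviation or power, because "we have no preliminary data to guide a power analysis".

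**The concern.** A paired t-test in a two-period crossover is free of the period effect only when the two orders have equal numbers. Here diagnosis is a unit of analysis in its own right, with its own recruitment target and its own tests, but nothing described in the plan makes the orders equal within a diagnosis.

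A period effect is plausible. VNeST is given at every treatment visit in both phases, so language gains in Phase I and Phase II can differ whatever the neurofeedback condition. The Phase I baseline is also the screening visit, where participants above 80% on the OANB are excluded. Regression after that selection would fall in Phase I only, most directly for the OANB.

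At stake are the estimate for each diagnosis and the comparison between diagnoses. Section 7c says the trial is meant to yield an effect size for planning a later trial, so error in the estimate actually obtained matters, and not only the average error rate.

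**Working it through.** **Plan's own figure.** Section 7c: "we plan to study 8 patients per year with post-stroke aphasia, and 8 patients per year with PPA". 8 × 5 years = 40 per diagnosis, 80 in total, which agrees with the stated target. There is no power or alpha figure to reproduce.

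**Assumptions.** Two-sided alpha of 0.05 (none is stated for the primary test). Period difference of 0.25, 0.5 or 1.0 SD, where SD is that of the within-patient difference within a sequence. The documents give no value.

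**Bias.** Let D = change under active minus change under sham, τ = the treatment effect, and π = Phase I change minus Phase II change. Then

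- active first: E(D) = τ + π
- sham first: E(D) = τ − π
- mean of all n patients: τ + π(n1 − n2)/n

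At 24:16 the fraction is 8/40 = 20%. At 26:14 it is 12/40 = 30%.

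**Chance of an uneven split, and its effect.** Probabilities are for that split or worse in one diagnosis of 40. Simple randomisation uses the binomial(40, 0.5). A list balanced 40:40 overall but not by diagnosis uses the hypergeometric(80, 40, 40). Type I error given the split comes from 100,000 simulated trials per cell with the unadjusted paired t-test. Triplets are for π = 0.25, 0.5 and 1.0 SD.

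| Split | Fraction | P, simple | P, balanced overall | Bias (SD) | Type I error |
|---|---|---|---|---|---|
| 20:20 | 0% | – | – | 0 / 0 / 0 | 0.043 / 0.028 / 0.006 |
| 22:18 | 10% | 0.636 | 0.503 | 0.025 / 0.05 / 0.10 | 0.046 / 0.037 / 0.017 |
| 23:17 | 15% | 0.430 | 0.264 | 0.0375 / 0.075 / 0.15 | 0.050 / 0.047 / 0.034 |
| 24:16 | 20% | 0.268 | 0.117 | 0.05 / 0.10 / 0.20 | 0.054 / 0.063 / 0.064 |
| 25:15 | 25% | 0.154 | 0.044 | 0.0625 / 0.125 / 0.25 | 0.060 / 0.083 / 0.116 |
| 26:14 | 30% | 0.081 | 0.013 | 0.075 / 0.15 / 0.30 | 0.067 / 0.106 / 0.192 |

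**Bias against standard error.** At 24:16 and π = 0.5, the unadjusted variance of D is 1 + 0.25 × (1 − 0.20²) = 1.24, so the standard error is √(1.24/40) = 0.176 SD. The bias of 0.10 SD is 0.10/0.176 = 0.57 standard errors.

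**Contrast between diagnoses.** If the list is balanced 40:40 overall, 24:16 in stroke forces 16:24 in PPA. A common period difference then shifts the stroke-minus-PPA contrast by 20% − (−20%) = 40% of its size.

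**Averaged over all splits.** Under simple randomisation the unadjusted test rejects at 0.050, 0.050 and 0.051 for the three values of π. With a list balanced overall the figures are 0.046, 0.039 and 0.024.

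**With period adjustment.** Averaging the two sequence means, with pooled SD and n − 2 degrees of freedom, gives a type I error of 0.049 to 0.051 at every split in the table. The variance relative to 20:20 is (1/24 + 1/16)/(2/20) = 1.042 at 24:16 and (1/26 + 1/14)/(2/20) = 1.099 at 26:14.

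**The case against.** **Silence is not evidence.** A reader might infer that order is randomised without stratification. The documents do not say so. Section 4c refers to a list of codes without describing how it is built, so it may already be blocked or stratified. This stands, and the point is limited to what is described.

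**The probability depends on the unstated method.** A reader might conclude that there is a 46% chance of 24:16 or worse in at least one diagnosis, from 1 − (1 − 0.268)² = 0.464. That holds only for simple randomisation. With a list balanced overall, the two diagnoses mirror each other and the figure is 12%. Both cases have to be shown.

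**Disease course is not in itself a period effect.** It is tempting to argue that PPA declines while chronic stroke is stable or improves, so the period effect must be large and opposite in the two groups. But the outcome is change within each phase, and each phase has 15 sessions. Steady decline or steady improvement adds about the same change to both phases and largely cancels. Only non-linear change, or phases of unequal length, leaves a difference. Learning and regression after screening remain plausible, but neither is quantified.

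**The consequence is limited.** A reader might infer that the tests by diagnosis have an inflated error rate. Averaged over simple randomisation they do not, and up to 23:17 the conditional error does not exceed about 0.05. These are supporting tests in a trial that calls itself preliminary.

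**Stratification alone is not the cure.** The root cause is the missing period term. A perfect 20:20 split leaves the plain paired t-test conservative (0.028 at 0.5 SD), and dropout can unbalance the orders again. This stands and shapes the fix.

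None of these removes the point. Where the split is uneven, the estimate for that diagnosis is shifted, and nothing in the planned analysis corrects it.

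**Conclusion.** The concern holds in a limited form. The plan describes no device to balance order within diagnosis and no analysis that would compensate for imbalance, yet it tests each diagnosis separately. At 24:16 one fifth of any period difference enters that diagnosis's estimate, which is 0.05 to 0.20 SD for assumed period differences of 0.25 to 1.0 SD. The type I error given the split is about 0.05 to 0.065 there, and about 0.07 to 0.19 at 26:14. The harm is conditional on the split obtained and modest.

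The result rests on the target of 40 per diagnosis, the assumed period differences and a two-sided 0.05 level. The pooled primary test is exposed in the same way but less: under simple randomisation the mean absolute imbalance is 8.9% of n at 80, against 12.5% at 40. Carryover after the one-week washout is a separate matter that neither stratification nor a period term resolves. This is a cheap improvement and does not threaten the trial's validity.

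**What to change.** 1. State how the order list is generated. For participants not yet randomised, use permuted blocks of random size stratified by diagnosis (post-stroke aphasia, PPA), aiming for about 20 per order in each.
2. Replace the plain paired t-test, overall and within each diagnosis, with a period-adjusted analysis. One form compares the Phase I minus Phase II differences in change between the two sequence groups and halves the result. This also covers participants already randomised and any imbalance caused by dropout, and it avoids the conservative test at 20:20.

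The cost is a different computer-generated list and one more term in the analysis. Allocation becomes slightly more predictable, which random block sizes limit. If the split is still uneven, the adjusted estimate loses about 4% in variance at 24:16 and 10% at 26:14, relative to 20:20.
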